5.2.4.5 Sensitivity Analyses

Performing the analysis described in Section 5.2.4.1 on the population of patients that showed up for the physical test. I. e. after the threshold imputation described in Section 5.2.4.4 has been performed.

5.2.4.6 Subgroup Analyses

No subgroup analyses will be performed.

5.2.5 Time to event secondary outcomes

Not applicable.

5.2.6 Additional Analyses

Not applicable.

6 Safety Analyses

Complications and adverse events were continuously registered. For instance, thromboembolic events, wound healing problems, infections and nerve-damage.

6.1 Adverse Events

Any complications and adverse events were continuously documented and any new rupture on the injured side (re-rupture) or the healthy side were immediately reported to the study coordinator. Re-ruptures are considered as a secondary outcome (see Section 5.1.3.2). Adverse events other than re-ruptures will be tabulated.

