1.1 Background and rationale

The management of acute Achilles tendon ruptures has been the subject of a long-standing debate. Contemporary rehabilitation protocols emphasizing early weight bearing and mobilization have furthermore blurred differences in treatment results. Open repair (OR) may reduce the risk of re-rupture, but at the expense of surgical complications such as delay in wound-healing and infection. This has led to the development of percutaneous and minimal invasive surgical techniques (MIS). The demonstration of significant differences comparing OR, MIS and conservative treatment (CT), requires a large sample, and although the previously reported differences have lacked statistical significance, they may be of substantial clinical value. We have therefore conducted a three-arm RCT comparing CT, OR and MIS that is sufficiently large to be able to demonstrate significant differences.

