3.1 Confidence Intervals and p-values

All calculated p-values will be two-sided and compared to a 5% significance level. If a p-value is less than 0.05, the null hypothesis in the test will be discarded. Efficacy estimates for the comparison of specific treatment arms will be presented with two-sided 95% confidence intervals. This trial utilizes a hierarchical testing procedure for the primary endpoint (see Section 2.4.1), which maintains the type I error rate at 5%.

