3.3 Analysis Populations

We define the following patient population in this trial.

- **All randomized patients:** All patients that have been randomized regardless if they actually received treatment or not.
- **Full analysis set (FAS):** All patients that are randomized, received treatment, and where ATRS was measured at least once post baseline (i.e. at 3 months, 6 months or 1-2 years). Patients are allocated to the treatment they were randomized to.
- **Per protocol set (PPS):** Similar to the FAS, but patients are allocated to the treatment they actually received.
- **Complete Case set (CCS):** The subset of patients in the FAS that has ATRS measurements at all follow-up visits. Patients are allocated to the treatment they were randomized to.

The FAS will be used for the primary analysis, while the PPS and the CCS will be used for sensitivity analyses.

4 Trial Population

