5.2.2 Dichotomous Secondary Outcome: Re-ruptures

5.2.2.1 Main Analysis

The probability of re-rupture will be compared pairwise between the three treatment groups.

A logistic regression model will be fitted to the data, where the treatment variable will be adjusted by study centre (the stratification factor used in the randomization). From the model, the estimated marginal means of the risk difference between the groups will be reported pairwise.

We expect that the number of re-ruptures will be low, which may lead to the normality approximation to the binomial distribution becoming questionable. If any of the expected numbers in one of the cells in the 3-by-2 contingency table, summarizing the number re-ruptures in the treatment groups, is less than 5, the following analysis will be performed in place of fitting the logistic regression model: The confidence intervals of the risk difference between the groups will pairwise be calculated using the Newcombe Hybrid Score[12]. Thus, the risk difference will not be adjusted for study centre.

The analysis will be conducted in the FAS.

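### Surgical complications, named in the rationale as the cost set against fewer re-ruptures, are only to be tabulated; pairwise risk differences with intervals in a named population would be a cheap improvement.

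*SAP*

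**What the plan says.** The rationale in SAP section 1.1 states the trade-off: "Open repair (OR) may reduce the risk of re-rupture, but at the expense of surgical complications such as delay in wound-healing and infection". It gives this as the reason percutaneous and minimally invasive techniques were developed.

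Re-rupture is a secondary objective (section 1.2.2). Section 5.2.2.1 analyses it with a logistic model adjusted for centre, from which "the estimated marginal means of the risk difference between the groups will be reported pairwise". If any expected cell count is below 5, the model is replaced: "The confidence intervals of the risk difference between the groups will pairwise be calculated using the Newcombe Hybrid Score".

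Section 6 says that complications were registered continuously and gives examples: "For instance, thromboembolic events, wound healing problems, infections and nerve-damage". Section 6.1 then fixes their analysis in one sentence: "Adverse events other than re-ruptures will be tabulated".

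Nothing elsewhere adds to this. The general rule in section 3.1 is confined to efficacy: "Efficacy estimates for the comparison of specific treatment arms will be presented with two-sided 95% confidence intervals". Section 5.2.6, Additional Analyses, is marked not applicable. Complications appear neither among the objectives in section 1.2 nor in the outcome overview in section 5.1.4.

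**The concern.** The rationale sets two quantities against each other, re-rupture and surgical complications, and the SAP plans an estimate of the between-arm difference for only one of them. A reader who wants to weigh a re-rupture difference between OR, MIS and CT against the complications would find a risk difference on one side and a table on the other.

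The table is also loosely specified. Section 6.1 does not say whether it counts patients or events, whether it is split by arm, what the denominator is, or which population it uses. The SAP is more exact about less important tables: section 3.2.2 has protocol deviations by treatment group with all randomised patients as denominator, and section 4.3 has baseline data by randomised arm with numbers and percentages.

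At stake is how well the report can describe the precision of the harm comparison. Also, if complications are compared later, the types chosen, the grouping and the population would be settled after the counts are known.

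**Working it through.** **Passages side by side**

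| | Re-rupture | Other complications |
|---|---|---|
| Named in the rationale (1.1) | yes | yes |
| Stated objective (1.2) | secondary | no |
| Between-arm estimate | pairwise risk difference (5.2.2.1) | none planned |
| 95% interval | explicit on the Newcombe route; on the logistic route it rests on 3.1 | none planned; 3.1 covers efficacy estimates only |
| Population | FAS (5.2.2.1) | not named |

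**Inputs**
- Arm size: 160 per group (completers, section 2.3), or 530/3 = 176.7, taken as 176 (targeted enrolment in section 2.3, 1:1:1 allocation in section 2.2).
- Event counts: the SAP gives no complication rates, so all counts below are assumptions, varied over a range.
- The SAP has no complication figure of its own to reproduce, and its sample size calculation concerns ATRS and does not enter here.

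**Formula (Newcombe hybrid score, the method named in section 5.2.2.1)**

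For each arm, with p = x/n and z = 1.96, the Wilson limits are

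l, u = [p + z²/(2n) ± z·√(p(1−p)/n + z²/(4n²))] / (1 + z²/n).

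With d = p₁ − p₂,

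lower = d − √((p₁−l₁)² + (u₂−p₂)²), upper = d + √((u₁−p₁)² + (p₂−l₂)²).

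**Worked example: 8 v 2 patients with an event, 160 per arm**
- p₁ = 5.00%, Wilson 2.56 to 9.56%. p₂ = 1.25%, Wilson 0.34 to 4.44%.
- d = 3.75 points.
- Lower = 3.75 − √(2.44² + 3.19²) = 3.75 − 4.02 = −0.3.
- Upper = 3.75 + √(4.56² + 0.91²) = 3.75 + 4.65 = 8.4.

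**Range (risk difference in percentage points, 95% interval)**

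| Assumed counts | 160 per arm | 176 per arm |
|---|---|---|
| 3 v 0 | 1.9 (−0.8 to 5.4) | 1.7 (−0.7 to 4.9) |
| 5 v 0 | 3.1 (0.2 to 7.1) | 2.8 (0.2 to 6.5) |
| 8 v 2 | 3.8 (−0.3 to 8.4) | 3.4 (−0.3 to 7.7) |
| 10 v 1 | 5.6 (1.6 to 10.5) | 5.1 (1.5 to 9.6) |
| 16 v 2 | 8.8 (3.8 to 14.4) | 8.0 (3.5 to 13.2) |

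The widths run from about 6 points (3 v 0) to about 11 points (16 v 2 at 160 per arm). The interval can be computed with no events in one arm, which matters because some surgical complications may be absent under CT.

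**Size of the addition:** 4 complication types × 3 pairs = 12 intervals. For comparison, section 5.1.3.4 counts 36 physical-test endpoints, and section 5.2.4.2 gives each pairwise differences with intervals: 36 × 3 = 108.

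**The case against.** The main objection is that nothing here is wrong. Complications are not an objective, the trade-off comes from the background section, and the stated primary question is ATRS superiority. Re-rupture has an estimate because it is a declared secondary outcome; safety data are conventionally tabulated. All of this stands, and it is why the point is offered as an improvement and not as a contradiction. What it does not answer is that the SAP's own rationale treats complications as the counterpart to re-rupture, and that the method needed is already in the SAP.

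Three stronger readings are tempting, and the document does not support them.

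- *A reader might infer that the trial will be unable to say whether complication rates differ.* The word used is tabulated, which does not exclude percentages, arms or denominators. From a table with patients and denominators by arm, anyone can compute the intervals above. What would be missing is a pre-planned comparison; the information itself would not be lost. Section 2.4.1 also already labels any test outside the primary hierarchy supportive or exploratory, which limits what a later comparison could claim.
- *A reader might infer that the analysis sets would drop patients with serious complications*, because the FAS in section 3.3 is limited to patients who "received treatment, and where ATRS was measured at least once post baseline", and the PPS and CCS build on it. No section applies these sets to adverse events, and section 3.3 also defines all randomised patients with no ATRS condition. Nothing shows that patients without an ATRS are those with early serious complications. What remains is only that no population is named.
- *A reader might infer that grouping as randomised would materially charge surgical complications to CT.* Assuming that 3% of CT patients are operated on and that the surgical complication risk is 8%, the effect is 0.03 × 0.08 = 0.24% of the CT arm, or 0.0024 × 176 ≈ 0.4 of a patient. That is immaterial, and sections 3.2.1 and 3.2.2 already report who received another treatment.

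The illustrative counts show only that the uncertainty is appreciable. Whether an interval excludes zero should not be read as a test.

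**Conclusion.** The point holds as a modest improvement. The SAP names surgical complications as the cost weighed against re-rupture, estimates pairwise differences for re-rupture, and plans only a table for the complications, with no estimate, interval, denominator or population. No figure in the SAP is wrong, and no conclusion about the primary outcome is affected.

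The size is the uncertainty that a table leaves unstated: intervals about 6 to 11 percentage points wide for the counts tried. This rests on arm sizes of 160 to 176 taken from section 2.3 and on assumed event counts, since the SAP gives no complication rates. The case does not rest on any claim of lost information, selective exclusion or material misattribution.

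**What to change.** Extend section 6.1 as follows.

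- For each of the four types listed in section 6 (thromboembolic events, wound healing problems, infections, nerve damage), report the number and percentage of patients with at least one event, by arm.
- Add the three pairwise risk differences with Newcombe hybrid score 95% intervals, as in section 5.2.2.1. Label them supportive, and perform no hypothesis tests.
- Name the population: all patients who received a study treatment, grouped by treatment received and regardless of whether an ATRS is available. Present the as-randomised table alongside.

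The cost is a few sentences in the SAP and a small addition to the safety tables. No data collection, significance level or sample size changes. The drawback is 12 further intervals without multiplicity adjustment, some of them based on very few events; the supportive label should be carried into the report so that none is read as a confirmatory result.

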6.2 Clinical Laboratory Parameters

Not applicable.

6.3 Vital Signs

Not applicable.

7 Statistical Software

All statistical analyses will be done using R version 3.6.3 (R Core Team (2020). R: A language and environment for statistical computing. R Foundation for Statistical Computing, Vienna, Austria. URL <https://www.R-project.org/>).

8 References

8.2 Reference to Data Handling Plan

Not applicable.
